4.0 Protocol Design

Twelve subjects meeting eligibility criteria will be enrolled. Throughout the study, the study therapists will maintain communication with the referring physician or therapist and any other health care providers requested by the subject. In consultation with their prescribing physician, any individuals taking psychiatric medications will taper off these medications, allowing for a washout period of at least 5 times the medication and active metabolite half-lives plus one week for stabilization before the experimental session. During the study, benzodiazepines or atypical antipsychotics may be used to alleviate severe distress or panic responses if other interventions are ineffective. Subjects who are in psychotherapy with an outside therapist at the time of enrollment may continue that therapy during the treatment period without increasing the number or type of sessions or changing type of psychotherapy until after the outcome assessment, one month after the second experimental session in Stage 1. After the treatment period, subjects may resume psychotropic medications and may change therapists or psychotherapy type.

Each of the 12 subjects will participate in two experimental MDMA-assisted therapy sessions of seven hours in duration within a brief course of non-drug therapy, including three preparatory sessions at the start of the study and three integrative sessions during the month after each experimental session. During preparatory sessions, subjects will learn what to expect during experimental sessions and complete pre-treatment assessments. The second preparatory session will include a comprehensive tour of the treatment location and introductions to all available research and support personnel who subjects are likely to see during experimental sessions. In-person visits will occur in a private room in an outpatient research facility. All in-person sessions after enrollment may be video recorded for the purposes of evaluating structural elements of therapy for effectiveness and feasibility. Video recordings will be used for research and training purposes during and after the study.

Upon enrollment, the first six subjects (Group 1) will be randomized to receive one dose of either placebo (N=2) or 75 mg MDMA (N=4). In the second experimental session one month later, Group 1 subjects randomized to MDMA will escalate to 100 mg MDMA, unless contraindicated by safety and tolerability concerns. The second six subjects (Group 2) will be randomized to receive one dose of either placebo (N=2) or 100 mg MDMA (N=4). In the second experimental session one month later, Group 2 subjects randomized to MDMA will escalate to 125 mg MDMA, unless contraindicated by safety and tolerability concerns. Subjects randomized to placebo in Group 1 and Group 2 will

receive placebo in both experimental sessions also scheduled one month apart. The blind will be maintained through the six-month follow-up for each individual subject, after which the blind will be broken. Placebo subjects will be offered an open-label extension (Stage 2) with two experimental sessions scheduled one month apart, in addition to three hour-long integrative sessions during the month after each experimental session. Stage 2 subjects will receive 75 mg MDMA in the first experimental session and will escalate to 125mg MDMA in the second experimental session, unless contraindicated by safety and tolerability concerns from other subjects in Stage 1.

During experimental sessions, there will be periods of structured and unstructured interactions. The structured interactions will be selected based on elements of therapeutic interventions that are currently in use in this population for the treatment of social anxiety and to enhance functional skills [7]. The unstructured interactions will include an array of therapeutic activities and approaches that would be appropriate for subjects to engage in during experimental sessions. All subjects will follow the same schedule of structured alternating with unstructured periods but will be able to choose from a selection of activities during each unstructured period. Examples include, but are not limited to, working with art supplies, listening to preselected music, writing in journals, silent introspection, and engaging in rapport-building interactions with researchers.

An overnight stay at a hotel located close to the site will be offered to subjects, accompanied by their support partners, if they live further than 30 miles from the site. Subjects will attend a 1-hour follow-up integrative therapy session on the day after the experimental session. Two additional integrative sessions will be conducted within the month following each experimental session, prior to outcome assessments being conducted one month after each experimental session. During integrative therapy sessions subjects will receive support in integrating their experiences and insights from the experimental session. The second experimental session will be scheduled approximately one month after the first experimental session, after outcome assessments have been completed.

All subjects, even those who have a prior diagnosis, will be clinically evaluated by the PI to determine autistic status. In addition, autistic status will be confirmed with the gold-standard diagnostic measure of autism and diagnosis of co-morbid psychological disorders will be conducted according to DSM-IV criteria at screening. Outcome measures will be assessed prior to treatment, during the treatment period, one month after each experimental session, and during the 6-month follow-up according to the Time and Events table. The sponsor will conduct an ongoing review of videos of therapy sessions, entry criteria, vital signs, and reaction data for completed sessions and any AEs. The sponsor will provide ongoing feedback to the co-therapist teams to ensure subject safety.

For all subjects blood samples will be obtained for biomarker analysis at baseline and during the study according to the Time and Events Table. Biomarker analyses including plasma OT, AVP, and CORT will be explored as surrogate endpoints at baseline, two hours after drug administration during the second experimental session, one month after the second experimental session, and at 6-month follow-up. Blood will be collected during the open-label extension Stage 2 two hours after drug administration during both

experimental sessions and one month after both experimental sessions. Biomarkers will be evaluated for predictive and prognostic power.

4.1 Planned Duration of Study

- Subjects in Stage 1 and follow-up: 8 months
- Subjects in Stage 1, follow-up, and Stage 2: 10 months

These lengths of time do not include screening, which may take up to two months. The total duration of the study will depend on enrollment rates, but is expected to last at least 22 months. Any delay between visits would result in a corresponding extension of study duration.

Table 2. Time & Events Stage 1

Study Phase	Baseline		Preparatory Sessions			Experimental Session	Integrative Sessions			Experimental Session	Integrative Sessions			Follow-up	6-Month Follow-up
	V1	V2	V3	V4	V5	V6	V7	V8	V9	V10	V11	V12	V13	(remote)	V14
Visit Timing			Week 1	Week 2	Week 3		1 day later	2 Wks later	2 Wks later	Apr. 1 Month after V6	1 day later	2 Wks later	2 Wks later	Monthly By Mail	6 Months after V10
Informed Consent	✓														
Medical/Psychiatric History & Evaluation	✓														
SCID	✓														
General Physical Exam (includes neurological)		✓													
Screening Clinical Lab Tests, EKG		✓													
ADOS-2		✓ ^H													
LSAS		✓ ^{G,H}					✓ ^G	✓ ^G	✓ ^G		✓ ^G	✓ ^G	✓ ^G		✓ ^G
C-SSRS		✓			✓	✓ ^{A,C,D}	✓ ^E	✓	✓	✓ ^{A,C,D}	✓ ^E	✓	✓		✓
Feedback Questionnaire, Qualitative Interview		✓													✓
Study Enrollment if Eligible			✓												
Collect Concomitant Medication	✓		✓	✓	✓	✓	✓	✓	✓	✓	✓	✓	✓		✓
Start Medication Taper (if applicable)			✓												✓ ^I
Collect Serology Samples (OT, AVP, CORT)		✓								✓			✓		✓
Record to Video			✓	✓	✓	✓	✓	✓	✓	✓	✓	✓	✓		✓
General Wellbeing			✓	✓	✓	✓	✓	✓	✓	✓	✓	✓	✓		✓
Pregnancy Screen (if applicable), Drug Screen		✓				✓				✓					
BDI-II, STAI			✓				✓	✓	✓		✓	✓	✓	✓	✓
PSS			✓				✓				✓		✓	✓	✓
IRI, RSES			✓				✓				✓		✓		✓
TASIT				✓		✓				✓			✓		✓
ERQ, TAS-20					✓								✓		✓
QoL-Q					✓										✓
Administer Drug + Therapy						✓				✓					
Monitoring of BP, Pulse, and Temperature, SUD						✓ ^{A,B,C}				✓ ^{A,B,C}					
Belief of Condition Assignment							✓				✓				
Integrative Therapy Session							✓	✓	✓		✓	✓	✓		
Start 7 Days Phone Contact							✓				✓				
Spont. Reported Reactions & All Adverse Events						✓	✓ ^F	✓		✓	✓ ^F	✓			
Symptoms at Baseline	✓		✓	✓	✓	✓	✓	✓	✓	✓	✓	✓	✓		✓
Adverse Events Requiring Doctor's Visit			✓	✓	✓	✓	✓	✓	✓	✓	✓	✓	✓		✓
Adverse Events Causing Withdrawal, SAEs			✓	✓	✓	✓	✓	✓	✓	✓	✓	✓	✓	✓	✓
Unblinding & Termination															✓ ^J
Approximate Hours for Study Visit	3	1.8	1.5	1.5	1.8	8.0	1.9	1.7	2.1	8.0	1.9	1.7	2.6	0	2.2

A = At the beginning of the session; B = Approximately every sixty minutes; C = As needed; D = Approximately six hours post drug; E = Day 2 and Day 7 phone calls only; F = Reactions collected for seven days post experimental session; G = Independent Rater administered; H = May be recorded to video; I = Stage 2 subjects only; J = Only MDMA subjects will terminate.

Table 3. Time & Events Stage 2

Study Phase	Experimental Session	Integrative Sessions			Experimental Session	Integrative Sessions		
	V15	V16	V17	V18	V19	V20	V21	V22
Visit #	V15	V16	V17	V18	V19	V20	V21	V22
Visit Timing		1 day later	2 Wks later	2 Wks later	Appr. 1 Month after V15	1 day later	2 Wks later	2 Wks later
LSAS		✓ ^G	✓ ^G	✓ ^G		✓ ^G	✓ ^G	✓ ^G
C-SSRS	✓ ^{A, C, D}	✓ ^E	✓	✓	✓ ^{A, C, D}	✓ ^E	✓	✓
Feedback Questionnaire, Qualitative Interview								✓
Collect Concomitant Medication	✓	✓	✓	✓	✓	✓	✓	✓
End Medication Taper (if applicable)	✓ ^I							
Collect Serology Samples (OT, AVP, CORT)	✓			✓	✓			✓
Record to Video	✓	✓	✓	✓	✓	✓	✓	✓
General Wellbeing	✓	✓	✓	✓	✓	✓	✓	✓
Drug Screen	✓				✓			
Pregnancy Screen (if applicable)	✓				✓			
BDI-II, STAI		✓	✓	✓		✓	✓	✓
PSS		✓				✓		✓
IRI, RSES		✓				✓		✓
TASIT	✓				✓			✓
ERQ, TAS-20								✓
Administer Drug + Therapy	✓				✓			
Monitoring of BP, Pulse, and Temperature, SUD	✓ ^{A, B, C}				✓ ^{A, B, C}			
Integrative Therapy Session		✓	✓	✓		✓	✓	✓
Start 7 Days Integrative Phone Contact		✓				✓		
Spont. Reported Reactions & All Adverse Events	✓	✓ ^F	✓		✓	✓ ^F	✓	
Symptoms at Baseline	✓	✓	✓	✓	✓	✓	✓	✓
Adverse Events Requiring Doctor's Visit	✓	✓	✓	✓	✓	✓	✓	✓
Adverse Events Causing Withdrawal	✓	✓	✓	✓	✓	✓	✓	✓
SAEs	✓	✓	✓	✓	✓	✓	✓	✓
Termination								✓
Approximate Hours for Study Visit	8.0	1.9	1.7	2.1	8.0	1.9	1.7	2.7

A = At the beginning of the session; B = Approximately every sixty minutes; C = As needed; D = Approximately six hours post MDMA; E = Day 2 and Day 7 phone calls only; F = Reactions collected for seven days post experimental session; G = Independent Rater administered; H = May be recorded to video; I = At least 5 half-lives and 1 week before the experimental session.

4.2 Recruitment and Subject Population

Subjects may be male or female, aged 21 or older, with a confirmed diagnosis of autism and two years of college-level education or comparable vocational training. Verbal and written proficiency in English will be required. Subjects communicating with text-to-speech technology will also be permitted. Therefore, the researchers anticipate that all subjects will have an AS diagnosis or a diagnosis of Autistic Disorder, as defined in the DSM-IV, coupled with strong verbal proficiency. Subjects must meet all protocol inclusion criteria and no exclusion criteria at baseline. Subjects must be in good physical health and without major medical disorders that might affect the safety or tolerability of MDMA. Subjects must be MDMA-naïve. Subjects will be asked to confirm that they will not take MDMA outside of the context of study participation during the study. Subjects will be recruited through printed advertisements, internet advertisements and discussion forums, referrals from other psychiatrists, psychotherapists or physicians, and through word-of-mouth.

4.2.1 Inclusion Criteria

Individuals eligible to be enrolled into this protocol are subjects who:

1. Be diagnosed with Autism Spectrum Disorder;
2. Have at least moderate to severe Anxiety;
3. Have had at least one unsuccessful attempt at treatment for PTSD either with talk therapy or with drugs, or discontinuing treatment because of inability to tolerate psychotherapy or drug therapy.
4. Are at least 21 years old;
5. Have completed two years of college-level education or comparable vocational training;
6. Must be generally healthy;
7. Must sign a medical release for the investigators to communicate directly with their therapist and doctors;
8. Are willing to refrain from taking any psychiatric medications during the study period;
9. Willing to follow restrictions and guidelines concerning consumption of food, beverages, and nicotine the night before and just prior to each experimental session;

10. Willing to remain overnight at the study site;
11. Agree to have transportation other than driving themselves home or to where they are staying after the integrative session on the day after the MDMA session;
12. Are willing to be contacted via telephone for all necessary telephone contacts;
13. Willing to give blood samples;
14. Must have a negative pregnancy test if able to bear children, and agree to use an effective form of birth control;
15. Must provide a contact in the event of a participant becoming suicidal;
16. Are proficient in speaking and reading English;
17. Agree to have all clinic visit sessions recorded to audio and video
18. Agree not to participate in any other interventional clinical trials during the duration of this study.

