2.3 Protocol Purpose

This is a double-blind, randomized, placebo-controlled, dose-finding Phase 2 pilot study designed to explore the safety and the therapeutic potential of MDMA-assisted therapy for treating social anxiety in 12 MDMA-naïve adults on the autism spectrum. This study will provide an estimate of effect size based on response to two experimental sessions of MDMA-assisted therapy in autistic adults on measures of safety, social anxiety, social perception, and psychiatric symptoms in comparison to a placebo control group. The primary outcome measure for the study will be the clinician-administered Liebowitz Social Anxiety Scale (LSAS) administered by a blinded Independent Rater (IR). Self-report measures will correspond to indications that often co-present with autism, including anxiety, stress, depression, emotion regulation, alexithymia, differences in some empathy domains, and other psychosocial challenges. Subjects will receive ongoing social support during the study in the form of non-drug therapy and active involvement of a support partner.

This study will employ biomarker analyses in combination with clinical outcome measures to provide useful insights into the underlying mechanism of MDMA's psychosocial and anxiolytic effects, and to examine any biological differences to treatment responses. The time course of biomarker concentrations will be used to determine if MDMA-assisted therapy causes lasting changes in biomarker levels in comparison to baseline.

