4.2.2 Exclusion Criteria

Individuals not eligible to be enrolled into this protocol are those who:

1. Are pregnant or nursing, or if a woman who can have children, those who are not practicing an effective means of birth control;
2. Weigh less than 48 kg;
3. Are abusing illegal drugs;
4. Are unable to give adequate informed consent;
5. Upon review of past and current drugs/medication must not be on or have taken a medication that is exclusionary.
6. Upon review of medical or psychiatric history must not have any current or past diagnosis that would be considered a risk to participation in the study.

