5.1.2 Outcome Measures

The primary outcome measure for the study will be the clinician-administered LSAS [130]. The LSAS is a 24-item, semi-structured interview on the severity of Social Anxiety Disorder, which has been widely used in clinical studies, including research on social anxiety in autistic adults [16]. The LSAS separately assesses fear (0 to 3 = none, mild, moderate, severe) and avoidance (0 to 3 = never, occasionally, often, usually) of 24 social situations, providing an overall social anxiety severity rating and subscale scores for performance fear, performance avoidance, social fear, and social avoidance. The overall scores are interpreted as: 55-65 moderate, 65-80 marked, 80-95 severe, and greater than 95 very severe social anxiety. The LSAS has been shown to have good internal consistency (score inter-correlations ranging from 0.81 to 0.96), reliability, convergent validity with other measures of anxiety, and sensitivity to treatment response. The LSAS was also demonstrated to be sensitive to the effects of pharmacological

treatments of social phobia in comparison to placebo and to have convergent validity [15]. A qualified blinded IR, who will not be present during experimental sessions, will complete the LSAS assessment. Subjects will be instructed not to inform the IR of any beliefs they or others have concerning their condition assignment during the assessment.

The BDI-II is a 1996 revision of the BDI, a 21-item self-report measure [131, 132], that will serve as a measure of depression according to DSM-IV criteria [133]. The BDI-II has been validated, has high internal consistency and good test/re-test reliability, and is not overly sensitive to daily variations in mood. It takes five to ten minutes to complete [133]. Score cutoffs indicate: 0-13 minimal depression, 14-19 mild depression, 20-28 moderate depression, and 29-63 severe depression. Higher scores indicate more severe depressive symptoms. The BDI-II will be completed according to the Time and Events table.

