5.2 Study Procedures and Visit Descriptions

5.2.1 Prescreening and Screening

The therapist team for this study will consist of the PI, [name]., and co-investigator [name]. Candidate, and all study visits will be completed at Harbor-UCLA Medical Center. Prospective subjects will be prescreened by telephone or email according to an IRB-approved script to learn if they meet basic eligibility criteria. All individuals who are prescreened should be assigned a screening number and recorded on the Subject Screening Log where information on the selection of potential subjects in the trial should be collected.

Upon signing the IRB-approved informed consent form (ICF), the potential subject may commence study-related screening activities. The screening number should also be recorded on the signed ICF. If a subject is enrolled, the study staff should record the enrollment date and assign a subject number. If a subject is not enrolled, an explanation should be recorded on the Screening Log. A CRF will not be completed for subjects who are not enrolled. These subjects will only be documented on the Screening Log and Source Records. It is the responsibility of the PI to file the Screening Log in the investigator site file (ISF) to be readily available for on-site monitoring and/or inspection by relevant authorities. Screening may take place over more than one day and should be complete by up to two months prior to enrollment. If, after reviewing all information, the PI concludes that a subject is eligible, they will enroll the subject in the study. Visits will be scheduled consecutively, as described in the Time and Events Table.

- a. Explain and obtain written informed consent from the subject and Support Partner. Written informed consent must be obtained from the subject prior to performing any tests or evaluations for the study.
- b. Assign the subject a screening number. Complete the Screening Log.
- c. Review the ability of females of childbearing potential to become pregnant and their commitment to practice appropriate birth control, as determined by the PI for the treatment period of the study.
- d. Collect perceptions about the study using the Feedback Questionnaire.
- e. Administer C-SSRS to assess suicide risk.
- f. Administer the SCID-I-RV to assess co-morbid psychological disorders.
- g. Administer ADOS-2, Module 4 to confirm autistic status.
- h. A blinded IR will administer the LSAS.
- i. Obtain medical and psychological history by interview.

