4.0 Study Design

This randomized, double-blind, placebo-controlled study will examine the safety, feasibility, efficacy of MDMA-assisted psychotherapy in twelve adults on the autism spectrum with social anxiety. Each of the 12 subjects will participate in two experimental drug-assisted (MDMA or placebo) therapy sessions of seven hours in duration within a brief course of non-drug therapy, including three preparatory sessions at the start of the study and three integrative sessions during the month after each experimental session.

Upon enrollment, the first six subjects (Group 1) will be randomized to receive one dose of either placebo (N=2) or 75 mg MDMA (N=4). In the second experimental session one month later, Group 1 subjects randomized to MDMA will escalate to 100 mg MDMA, unless contraindicated by safety and tolerability concerns. The second six subjects (Group 2) will be randomized to receive one dose of either placebo (N=2) or 100 mg MDMA (N=4). In the second experimental session one month later, Group 2 subjects randomized to MDMA will escalate to 125 mg MDMA, unless contraindicated by safety and tolerability concerns. Subjects randomized to placebo in Group 1 and Group 2 will receive placebo in both experimental sessions also scheduled one month apart. The blind will be maintained through the six-month follow-up for each individual subject, after which the blind will be broken. Placebo subjects will be offered an open-label extension (Stage 2) with two experimental sessions scheduled one month apart, in addition to three hour-long integrative sessions during the month after each experimental session. Stage 2 subjects will receive 75 mg MDMA in the first experimental session and will escalate to 125mg MDMA in the second experimental session, unless contraindicated by safety and tolerability concerns from other subjects in Stage 1. Subjects will attend a 1-hour follow-up integrative therapy session on the day after the experimental session. Two additional integrative sessions will be conducted within the month following each experimental session, prior to outcome assessments being conducted one month after each experimental session.

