6.0 Sample Size and Power Considerations

This study is a pilot investigation intended to gather preliminary data on the safety and efficacy of MDMA in 12 subjects on the autism spectrum with social anxiety. Because of their exploratory nature, pilot studies are often not powered for detecting the desired effect. Because it is a pilot study in a small sample, results will be used to collect effect size estimates for statistical power calculations for adequately powered subsequent studies.

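### Inclusion criterion 2 asks for anxiety in general and sets no LSAS minimum, although the population is defined by social anxiety and the primary endpoint is LSAS change

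*Protocol*

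**What the plan says.** Protocol 4.2.1, criterion 2, requires that candidates "Have at least moderate to severe Anxiety". Protocol 4.2 makes the list binding: "Subjects must meet all protocol inclusion criteria and no exclusion criteria at baseline". The exclusion list (4.2.2) has one psychiatric item, and it concerns risk only: a candidate "must not have any current or past diagnosis that would be considered a risk to participation in the study".

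The stated target is narrower. Protocol 2.3 describes "MDMA-assisted therapy for treating social anxiety in 12 MDMA-naïve adults on the autism spectrum". SAP 4.0 describes "MDMA-assisted psychotherapy in twelve adults on the autism spectrum with social anxiety", and SAP 6.0 speaks of preliminary data "in 12 subjects on the autism spectrum with social anxiety". Protocol 3.1 makes the LSAS effect size the primary objective, and SAP 8.10.1 tests LSAS change from baseline to Visit 13.

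The information needed for a sharper rule is already collected. Protocol 5.2.1 lists, among the screening steps, "A blinded IR will administer the LSAS". Protocol 5.1.2 supplies severity bands: "The overall scores are interpreted as: 55-65 moderate, 65-80 marked, 80-95 severe", with scores above 95 called very severe. Neither the screening score nor the bands are tied to entry.

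**The concern.** The entry rule names a broader construct than the endpoint measures. Someone whose anxiety is mainly not social can satisfy criterion 2 as written, whatever the LSAS shows. If that person also meets the remaining criteria, no written rule keeps them out.

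Three things are at stake:

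- **Effect size.** A subject who starts low on the LSAS can improve little. In a trial of 8 against 4, one or two such subjects can move the estimate noticeably, and SAP 6.0 intends that estimate for later power calculations.
- **Population.** The result would not cleanly describe adults with social anxiety, the group the SAP says was studied.
- **Per-protocol set.** SAP 8.4 counts enrolment of someone who fails the entry criteria as a major deviation that removes them from the per-protocol analysis. With criterion 2 this open, neither a monitor nor the statistician could apply that rule objectively to a low scorer.

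**Working it through.** **Text check.** I looked for a social-anxiety or LSAS requirement wherever one could sit.

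- Protocol 4.2 (recruitment): autism diagnosis, age, education, MDMA-naïve status, health. No mention of social anxiety.
- Protocol 4.2.1: criterion 2 is the only anxiety item. Criterion 3 concerns earlier PTSD treatment, or treatment stopped because it was not tolerated.
- Protocol 4.2.2: none.
- Protocol 5.1.1 and 5.2.1: the SCID assesses co-morbid disorders, with no required diagnosis. The LSAS is scored with no threshold.
- Protocol 5.2.2: eligibility is confirmed at Visit 3 against the same lists.
- SAP 8.1: no analysis population has a baseline LSAS condition.

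The requirement is absent throughout.

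**Scale of the consequence.** Protocol 12.1 says no power estimate was available, and neither document gives an effect size or SD, so there is no planned figure to reproduce. The LSAS total runs from 0 to 24 × 2 × 3 = 144 (24 situations, two ratings, each 0–3).

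Assumptions: a true standardised difference D among subjects with room to improve; no mean change on placebo; k low scorers with zero mean change; arms of 8 and 4.

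*Model A: low scorers spread evenly over the arms, SD held at 1.* d = D(1 − k/12).

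- D = 1.5: k = 1 gives 1.5 × 11/12 = 1.375, about 1.38 (−8%). k = 2 gives 1.5 × 10/12 = 1.25 (−17%).
- D = 1.0: 0.92 and 0.83.

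*Model B: all low scorers in the MDMA arm, with the mixture inflating the SD.* MDMA mean = D(1 − k/8). Pooled variance = [7 + 3 + 8(k/8)(1 − k/8)D²]/10.

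- D = 1.5, k = 1: mean 1.3125; variance (10 + 1.969)/10 = 1.197; d = 1.3125/1.094 = 1.20 (−20%).
- D = 1.5, k = 2: mean 1.125; variance (10 + 3.375)/10 = 1.3375; d = 1.125/1.1565 = 0.97 (−35%).
- D = 1.0: 0.84 and 0.70.

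*Variant of B: low scorers also have no variance in their change scores.* Pooled variance = [(8 − k)(7/8) + 8(k/8)(1 − k/8)D² + 3]/10.

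- D = 1.5, k = 1: (6.125 + 1.969 + 3)/10 = 1.109; d = 1.3125/1.053 = 1.25.
- D = 1.5, k = 2: (5.25 + 3.375 + 3)/10 = 1.1625; d = 1.125/1.078 = 1.04.

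Under the 4:2 split in each group of six, one low scorer lands on MDMA with probability 4/6 = 67%. Two both do so with probability (4/6)(3/5) = 40% if they are in the same group, or (4/6)(4/6) = 44% if in different groups. Model B is thus the less favourable allocation, but not a remote one.

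**Against sampling error.** The approximate SE of d is √[12/32 + d²/24], which at d = 1.5 is √(0.375 + 0.094) = 0.68. The shifts in Models A and B at D = 1.5 run from 0.125 to 0.53, roughly 0.2 to 0.8 of one SE.

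**The case against.** **The intent is recoverable.** Both documents speak of social anxiety, the severity words in criterion 2 echo the LSAS bands in 5.1.2, and a single investigator at one centre enrols after reviewing all screening information (5.2.1). A low scorer might well be turned away in practice. This stands as a reason to expect few such entrants. It does not supply a written rule, and criterion 3, which refers to PTSD, shows that the list was not fully aligned with this indication.

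**The posted list may be condensed.** Protocol 7.2.1 and 7.2.2 mention exclusions for hypertension, bipolar I and psychotic disorders that 4.2.2 does not itemise. A threshold could have operated elsewhere. That is possible, but neither document contains one.

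**The dilution is hypothetical and smaller than sampling error.** This is correct. The effect sizes and the number of low scorers are assumed, and each shift is less than one SE. Dilution is nevertheless a systematic pull, and it can be avoided at little cost.

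**Effect size is not the only aim.** Protocol 12.0 calls this primarily a safety study, and SAP 2.0 puts effect size second. The safety aim is not weakened by this point. Protocol 3.1 still makes the LSAS effect size the primary objective.

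A reader might infer two stronger claims that the documents do not support. The first is that the list by itself would admit any autistic adult with, say, generalised anxiety and a very low LSAS. All criteria must be met, and criterion 3 is a further hurdle for that person. The second is that a SCID diagnosis could never close the gap, because DSM-IV criterion G (Protocol 2.2.2) rules out fear better accounted for by a pervasive developmental disorder. That is a case-by-case judgement, and the same section treats social anxiety as a frequent co-morbidity in autistic adults. A SCID diagnosis would be an uncertain substitute, but not an impossible one.

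**Conclusion.** The point holds as a mismatch between entry rule and endpoint. Criterion 2 does not require social anxiety or any LSAS level, and nothing else in the two documents does. Low-LSAS subjects who meet the other criteria could be enrolled, and they would tend to pull the effect-size estimate down.

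The direction is clear, but the size is not known. At an assumed d of 1.5, one or two low scorers among 12 bring it to 1.38 or 1.25 under even spread, and to 1.20 or 0.97 if all are on MDMA. These figures rest on assumed effects, zero mean change in low scorers and no mean placebo change. The documents do not show that any such subject was enrolled, nor that the Model B loss is the expected one. This should be fixed; it is not a fatal flaw.

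**What to change.** Reword criterion 2 to require social anxiety of at least moderate severity, judged by the independent rater's LSAS total at Visit 2, and check it at the Visit 3 eligibility review. The lower bound of the moderate band in Protocol 5.1.2 (55) is the natural cut because it is the protocol's own. No passage ties a band to entry, however, so the sponsor must adopt it explicitly. Reconcile criterion 3 with the trial's indication in the same amendment.

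The change needs no new visit, instrument or staff, since Table 2 already places the LSAS at Visit 2 and enrolment at Visit 3. It has three costs:

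- Recruitment may be slightly slower.
- The Visit 2 LSAS is also the baseline for the change score (SAP 8.6), so selecting on it brings some regression to the mean. This inflates within-arm change, but randomisation makes it equal in expectation in both arms. Within-arm changes should be read with that in mind.
- Visit 2 precedes any medication taper, which starts at Visit 3, so some candidates would be judged on scores obtained while still medicated. The protocol should acknowledge this.
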